11. RISKS TO SUBJECTS

Participants may experience psychological risks associated with participation in this study, such as discomfort or boredom in answering questions or providing feedback about the app. There is also a risk of loss of confidentiality. All data collected for the proposed research study will be kept confidential to the extent allowed by law. Although it is unlikely given the nature of this study, if participants disclose that someone is being maltreated or is a danger to self or others, research staff will need to break confidentiality to make a report to the appropriate authority to ensure safety, as mandated by law. We believe that all identified risks are reasonable given the proposed procedures for protecting against risk.

Protections Against Risks

To minimize risk associated with psychological discomfort, participants will be given the option to skip questions they feel uncomfortable answering. Multiple procedures will be implemented to protect participant confidentiality. In terms of data storage and management, any hard copy data will be secured in locked file cabinets within locked offices, available only to program staff. Electronic data will be stored on URMC managed Box folder for this project, and only project staff with appropriate permissions will be able to access the data. Forms with

Page 7 of 13

identifying information will be separated from the data collected and only subject numbers will be retained in data analysis files.

Multiple levels of protection will be put in place to reduce the risk of loss of confidentiality for data collected through the app. A local datastore will protect the mobile application against network failures and connectivity issues. This local datastore will be transparently synchronized with the Cloud database so that all the querying and security features will be always available regardless of network connectivity. Collected data will be stored using a random code that will not allow direct identification of a particular subject, while any data that identify the user will be stored separately. All the connections between the mHealth app and the Cloud, as well as access and storage to the Cloud database, will use state of the art authentication and encryption algorithms (e.g., HTTS, SSL and TLS). The Cloud architecture and services will be built and are managed by [name], under a University-managed Cloud account, and in compliance with University policy. Security and Benchmark compliance reports generated by Lacework will be received and reviewed daily by [name]. Access to the data stored on the Cloud will be restricted, access to the data with be logged and backups will be created to allow the users to restore them if/when necessary. Appropriate policies will be set up so that users will be able to add and modify their own data but will be prevented from viewing and modifying other users' data. My Health Coach will also not alter the security settings of the user's phone, access stored information in the phone, or access device functionalities without explicit user consent. A passcode (or touch ID/Face ID) will be required to access the content of the app, and all the personal data stored by the app will be encrypted automatically whenever the device is locked.

All information obtained for research will be kept strictly confidential (as allowed by law) by research staff. Participants will be told about all exceptions (e.g., child/dependent adult abuse, harm to self or others) to confidentiality during the consent process. Project staff will be closely supervised by [name] and instructed on confidentiality, including what information is confidential, the limits of confidentiality, and to whom to report concerns.

The My Health Coach app is viewed as a "value-added" intervention. Participants can continue to receive care as usual in their community. The alternative to participating in this study is not to participate.

12. POTENTIAL BENEFITS TO SUBJECTS

Participants may not experience any direct benefits from participating in this study. However, participants in prior FASD research studies at MHFC have commented on how they value and derive personal satisfaction in participating in research to increase knowledge about this underrecognized condition and effective strategies to benefit other people with FASD. It is also possible, although not guaranteed, that participants might derive benefit from using the My Health Coach app. Possible benefits may include improved self-management, advocacy, and quality of life.

13. COSTS FOR PARTICIPATION

There are no costs to participate.

Page 8 of 13

14. PAYMENT FOR PARTICIPATION

Participants will receive a \$25 gift card for completing: baseline surveys, 6-week follow-up surveys, and the qualitative interview, for a possible total of \$75 if all activities are completed.

15. SUBJECT WITHDRAWALS

Subjects will be advised during the consent process that they have the right to withdraw from the study at any time without prejudice. They can choose to use the app as much as they want (or not at all). We are interested in obtaining survey data as well as feedback about the user experience from as many participants as possible, including those who chose not to use the app or found it hard to navigate. This information is useful in identifying ways to improve the app and facilitate user engagement. Subjects can choose not to complete any or all of the study assessments. They can also completely withdraw from the study with no future contact if they choose. In this case, any data they have previously provided may be used in analyses.

16. PRIVACY AND CONFIDENTIALITY OF SUBJECTS AND RESEARCH DATA

All data will be used solely for research purposes and will be securely locked in designated file cabinets, URMC managed Box folder dedicated to project, Project REDCap database, and an encrypted, HIPAA-complaint Cloud database (AWS; for data collected via the app; see above). Identifying information will be stored separately from other data, which will be stored by research ID number (GUID). Multiple procedures will be implemented to protect participant data collected through the app, which are further detailed in the section "Protections Against Risks" and Data Security Assessment form. Only senior key personnel and project research staff will have access to the data.

The following table summarizes the project data flow. MHFC IT will set up and manage permissions for URMC Project Box folder. Only project staff will have access to REDCap and Box folders. [name] will coordinate with the CIFASD5 Coordinating Center to facilitate required data uploads to NIAAA-Data Archive as required by the grant for eligible de-identified data (pre-post surveys; all other data exempt).

Data Element	How Data	Where Data is	How Data is Managed
	Collected	Stored	
Information	REDCap	REDCap, Back-ups	MHFC IT; Project Staff
Sheet,		URMC Box	
Screening			
Survey,			
Contact			
Information			
Legal Guardian	REDCap	REDCap, Research	MHFC IT; Project Staff
Permission		staff signed copy of	
Form		permission form on	
(eConsent)		URMC Box	
Baseline (T1)	REDCap	REDCap, Back-ups	MHFC IT; Project Staff;
Surveys		URMC Box,	CIFASD5 Coordinating
		CIFASD/NIAAA-DA	Center
6-week	REDCap	REDCap, Back-ups	MHFC IT; Project Staff;

Page 9 of 13

Follow-up (T2)		URMC Box,	CIFASD5 Coordinating
Surveys		CIFASD/NIAAA-DA	Center
Follow-up	Zoom, back-	URMC Box	MHFC IT; Project Staff;
Interview	up audio		Audio/video data is
	recording		transcribed verbatim;
			audio/videos deleted once
			transcript verified
My Health	User device	URMC-managed	Access is restricted to
Coach App	synchronized	account on AWS	authorized individuals and
usage data and	with AWS		every access to the data will
User's inserted			be logged, data is encrypted
data			in transit and at rest. AWS
			account is set up in
			compliance with UR/URMC
			policies and monitored by
			Lacework.

15. DATA / SAMPLE STORAGE FOR FUTURE USE

All data (de-identified and identifying) will be securely stored locally for an indefinite period. De-identified and identifying information will be stored separately as detailed above. Novel research questions may arise in the future that this important dataset could answer. Future studies may also be interested in long-term follow-up of individuals who participated in this research. Retaining identifying information would facilitate contacting individuals (subsequent to new IRB approval) to see if they would be interested in participating in follow-up research. MHFC has well-established data security procedures in place for long-term storage and maintenance of data. Only approved project staff will have access to data.

De-identified pre-post data from this study will also be submitted to the National Institute on Alcohol Abuse and Alcoholism Database (NIAAA_{DA}) at the National Institutes of Health (NIH), as required. As a CIFASD Project, the CIFASD5 Data Coordinating Resource will facilitate required timely data harmonization and uploading to the NIAAA_{DA}. Recommended language has been included in the Information Sheet and Permission forms, including a link to more information about the data archive and sharing policies: https://nda.nih.gov/niaaa.

16. DATA AND SAFETY MONITORING PLAN

Because the research involves the provision of a mobile health intervention for adults with FASD, the risk for a serious adverse event due to provision of the intervention is low. Adverse events that could occur in adults with FASD could include aggression or violence towards others, maltreatment, self-harm or suicidality, or the need for inpatient hospitalization. However, these occurrences are unlikely to be a direct consequence of participation in the proposed research or interventions.

[name] will assume ultimate responsibility for the safety and well-being of research participants and the integrity of data collected. [name] has conducted several RCTs with children and adults with FASD and their families. She is a licensed psychologist in the state

Page 10 of 13

of New York and is involved in other clinical and research activities at MHFC where maltreatment and suicidality are commonly reported.

The well-being of participants will be monitored throughout the course of the proposed research. If there are concerns regarding a participant during interactions with research staff, staff will immediately contact [name] for consultation and a plan will be developed to address the concerns raised. Additionally, because MHFC provides other treatment programs, there are other back-up clinical supervisors available for consultation for immediate needs. A phone tree will be established, similar to other projects at MHFC, and will be provided to research staff. [name] will meet with research staff at least weekly to provide supervision and will assess participant well-being. [name] will consult with other co-Investigators and clinical staff at MHFC, as appropriate, to address participant well-being concerns.

An independent safety monitoring board has also been established for the larger project, consisting of researchers and clinicians with relevant expertise with at-risk populations, clinical trial monitoring, and human subjects protections and technology. ISM members and their areas of expertise are listed in the following table:

Name	Title & Affiliation	Relevant Areas of Expertise & Experience
[name]	Director & Professor, Mt.	Clinical psychologist; developmental
[name], Ph.D.	Hope Family Center,	psychopathology; relational
	University of Rochester	interventions; maternal depression;
		maltreatment; prevention of teen
		depression; has conducted multiple
		large-scale intervention trials with
		high-risk populations.
[name],	Clinical Director, Kirch	Pediatric nurse practitioner; physical
M.S. PNP	Developmental Services	and mental health of children with
	Center,	developmental disabilities; intellectual
	Neurodevelopmental and	disability, FASD, autism, and cerebral
	Behavioral Pediatrics,	palsy.
	University of Rochester	
	Medical Center	
[name]	Associate Professor in	Clinical psychologist; suicide
[name],	Psychiatry and Pediatrics,	prevention; public health messaging;
Ph.D.	Center for the Study and	safe and ethical use of technology in
	Prevention of Suicide,	prevention science
	University of Rochester	
	Medical Center	

The ISM committee will review and suggest modifications to research protocols and consent documents to assure scientific integrity and adherence to human subjects' protection policies. They will meet with the PI and co-Investigators twice a year to monitor safety issues and provide feedback on scientific and ethical issues relating to project implementation. The IRB will be notified immediately of any adverse events via telephone and submission of a

Page 11 of 13

"University of Rochester Serious Adverse Event Report". Such events would also be reported to NIAAA. The proximity of committee members will also facilitate their ability to monitor data management activities. The committee may ask to review data for quality control purposes.

Ethically, we are committed to ensuring the welfare of people with FASD. Any significant mental health or safety issues detected during the conduct of this investigation will be discussed with participants and options for the receipt of services presented.

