4. STUDY DESIGN

Page 2 of 13

This feasibility study will use a single group design with assessment timepoints prior to the receipt of the app and 6-weeks later. Primary outcomes assessed will include quality of life, self-determination theory constructs (i.e., autonomy, competence, relatedness), self-management, and barriers to care. Acceptability of the app and trial procedures will also be assessed at the 6-week timepoint.

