9. STUDY PROCEDURES

The project research assistant will track participants in REDCap once enrolled and will facilitate timely completion of research assessments. All participants will be encouraged to complete assessments, regardless of their level of engagement with the My Health Coach app. Actual user data from the app (whether minimal or extensive) will be important in addressing study aims.

After informed consent, participants will be asked to complete a set of baseline surveys (see details on the assessment battery below). To be most sensitive, given the unique neurobehavioral profiles of participants, administration will be flexible based on participant needs and can include surveys completed independently online, over the phone or Zoom with research staff, or through the mail. Afterwards, they will be provided information on how to install the app on their phones. Study staff will be available to troubleshoot problems with installation or app use. After 6 weeks, all participants will be re-contacted to complete follow-up surveys. User implementation data will be gathered through the app. To further assess acceptability, satisfaction, and barriers and facilitators of app use, the study research assistant will complete qualitative interviews with participants over HIPAA-complaint Zoom or telephone. Interviews will be recorded and later transcribed verbatim.

Study Assessment Battery

Measure	Baseline	6-Week
		Follow-up
Quality of Life: Personal Well-being Index – Intellectual	X	X
Disability Version		
Self-Determination: The Basic Psychological Need	X	X
Satisfaction and Frustration Scale		
Self-Management	X	X
Barriers to Healthcare Checklist	X	
FASD Education	X	
Basic Demographics	X	
Acceptability: Theoretical Framework of Acceptability		X
measure		

Page 6 of 13

Qualitative Interview on User Experience		X
--	--	---

Qualitative Interview. The semi-structured questioning route will cover the following topics: 1) overall impressions of My Health Coach; 2) experience using the app (both facilitators and barriers of use); and 3) perceived impact on their health and well-being. Interviews are expected to last about 30 minutes.

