My Health Coach app. The My Health Coach app is designed to offer adults with FASD evidence-based education about their condition and tools to promote their own self-management and health advocacy goals. It uses a chatbot interface to engage with users and help navigate through the app features. The user will be able to customize their chatbot as well as their own avatar to ensure they feel comfortable while using the app. Key features include a daily check-in, which records mood, physical health symptoms, sleep quality, and positive activities completed each day. Daily answers can be referred back to as needed. The app also includes a tracker the user can cusstomize to track things such as medication or daily tasks. Next, the app will also include a library where users can access evidence-based factsheets on their condition and strategies to aid with condition management. Lastly, the app will send a daily message notification. These will include strategies, FASD facts, and positive affirmations.

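### The protocol promises continuous monitoring of well-being but lists no means of eliciting the events it names, so a zero or low event count could not be interpreted

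*Combined protocol and SAP*

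**What the plan says.** The Data and Safety Monitoring Plan (the second of two sections numbered 16) makes a general commitment: "The well-being of participants will be monitored throughout the course of the proposed research". It names the events that could occur in this population as "aggression or violence towards others, maltreatment, self-harm or suicidality, or the need for inpatient hospitalization", and considers them unlikely to result directly from the research.

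The trigger for action is "If there are concerns regarding a participant during interactions with research staff". An investigator also meets research staff at least weekly, and participant well-being is assessed as part of that supervision. Downstream, "The IRB will be notified immediately of any adverse events via telephone", events go to the funder, and a safety committee meets twice a year.

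The procedures are in Sections 4 and 9:

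- **Timepoints.** Section 4 describes a "single group design with assessment timepoints prior to the receipt of the app and 6-weeks later".
- **Contact.** After installation, staff help with technical problems on request. The next scheduled contact is at week 6: "After 6 weeks, all participants will be re-contacted to complete follow-up surveys".
- **Survey mode.** Surveys may be done alone online or by post, as well as live with staff.
- **Battery.** The table lists no adverse-event measure at either timepoint. The nearest entries are a well-being index, classed as quality of life, and a week-6 interview. One interview topic is how users feel the app affected their health and well-being.
- **App data.** "Key features include a daily check-in, which records mood, physical health symptoms, sleep quality, and positive activities completed each day". Section 16 on privacy says app data synchronize to the study's cloud account. No section says that anyone reads them for safety.

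**The concern.** The monitoring commitment covers the whole study, but the detection route works only when a participant and a staff member happen to interact and something of concern comes up. For six weeks no such interaction is scheduled, and the surveys at either end may involve none. Committee review and ethics-board notification act only on events already detected, so they cannot make up for events that never reach staff.

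What is at stake is how any safety statement is read. Sections 1 and 17 say the data will inform a larger randomized trial. If the investigators tell the committee, or write in the next protocol, that few or no events occurred, nobody could say whether few happened or few were heard about.

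**Working it through.** **Step 1: is there a figure to reproduce?** There is no safety figure. The documents give no expected event rate, and Section 17 plans no event count. The only usable numbers are in Section 5: enrol 48 to obtain 40 with complete data, an implied loss of 1 − 40/48 = 16.7%.

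**Step 2: could each stated element detect an event between installation and week 6?**

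| Element | Where | Can it detect an event? |
|---|---|---|
| Staff escalation | Safety plan | Only if an interaction happens and the event surfaces |
| Weekly supervision | Safety plan | Meeting is with staff, so it relays only what they have heard |
| Technical help | Section 9 | Started by the participant, on technical matters |
| Surveys | Section 9 | No event item listed; may be unattended |
| Week-6 interview | Section 9 | Live contact; one topic may surface events, but the named events are not listed as topics |
| Daily check-in | Section 9 | Holds mood and symptoms; no safety review stated; app use is optional (Section 15 on withdrawals) |
| Safety committee, ethics board | Safety plan | Act only after detection |

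No row describes systematic elicitation of the named events.

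**Step 3: how far could a zero count mislead?** Let p be the true proportion with any listed event over 6 weeks and s the share of those events that reaches staff. Both are assumptions, shown as ranges. With n = 48, the chance of recording none is

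P(0) = (1 − p·s)^48.

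At p = 10%, 48 × 0.10 = 4.8 participants with an event are expected:

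- s = 1: 0.900^48 = 0.6%
- s = 0.5: 0.950^48 = 8.5%
- s = 0.25: 0.975^48 = 29.7%
- s = 0.1: 0.990^48 = 61.7%

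For other true rates, in the same order of s:

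- p = 5%: 8.5%, 29.7%, 54.7%, 78.6%
- p = 20%: 0.002%, 0.6%, 8.5%, 37.9%

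**Step 4: what would a zero count exclude?** With everyone asked and every event captured, the exact one-sided 95% upper bound is 1 − 0.05^(1/n):

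- n = 40: 7.2%
- n = 48: 6.1%

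The n = 40 figure suits a week-6 question, because 40 is the expected number with complete data. It assumes all 40 take the interview.

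If only a share s is captured, the bound applies to p·s, so the bound on p is the value above divided by s:

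- s = 0.5: 14.4% (n = 40) or 12.1% (n = 48)
- s = 0.25: 28.9% (n = 40) or 24.2% (n = 48)

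The documents give no basis for choosing s, so under the current plan none of these bounds can be claimed.

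**The case against.** The study is described as minimal risk, and the safety plan rates the risk of a serious event caused by the app as low. How intensively to elicit events is therefore partly a matter of judgment. Some monitoring is also stated: the weekly meeting, a live week-6 interview with a relevant topic, and a rule on disclosures of maltreatment or danger in the section on risks. These deserve credit, and they support treating this as a recommended improvement rather than a fatal flaw. They do not supply elicitation or fill the six-week interval.

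A reader might infer more than the documents support:

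- **That participants are never asked about adverse events.** The survey forms and the full interview guide are not in the documents. What can be said is that no such item is listed.
- **That a low count would be an artefact.** It could be true. The calculation shows that a low count would be ambiguous, not that it would be false.
- **That a biased event rate will be reported.** Section 17 plans no event count or rate. The consequence attaches to any safety statement passed on, and in a single-group study even a complete count could not separate app effects from background events.
- **That zero recorded events excludes nothing.** Under a known capture share it excludes something, as Step 4 shows. No bound is available because the share is unknown.

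**Conclusion.** The point holds as a mismatch between the monitoring commitment and the listed procedures. Followed as written, the plan captures the events it names passively and incompletely, and a zero or low count could not be distinguished from under-ascertainment.

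The size depends on two assumed quantities. With 48 participants and a 10% true rate, the chance of recording nothing runs from 0.6% (full capture) to 61.7% (one tenth captured). Systematic asking at week 6 would turn a zero count into a usable statement: at most 7.2% with 40 asked, or 6.1% if all 48 are, provided that those asked report accurately. Minimal risk and the absence of a planned safety analysis limit the severity, but the passages still need to be reconciled.

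**What to change.** 1. At the existing week-6 interview, ask every participant a short standard question set: has any of the events already listed in the safety plan occurred since baseline? The interview is a live staff contact, so answers fall within the escalation route as written.
2. Add to Section 17 a descriptive count of these events, with the number asked as denominator and the number not asked shown beside it.
3. If the items are also placed in the week-6 survey, the documents must first reconcile how answers given with no staff present enter the escalation route, whose trigger is limited to staff interactions.
4. State whether daily check-in entries are reviewed for safety, and align the monitoring commitment with what is done.

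This needs no new visit. The cost is a slightly longer interview, an ethics-board amendment and some positive answers to process. Participants who skip the interview, as Section 15 on withdrawals allows, would still contribute no information.
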